## **(2) Adequacy of Protection from Risks**

(a) Recruitment and Informed Consent: Participants will be recruited from the MIRECC Mild TBI/Behavioral Specialty Clinic; Deployment Health Clinic, Polytrauma Clinic, General Internal Medicine Clinic, and Mental Health Clinics at the VA Puget Sound; the Seattle downtown Vet Center; CBOCs, and from outreach to National Guard and Reserve units. Recruitment will be assisted by posters, flyers, brochures,

announcements in the VA daily bulletin, and print and radio media advertising. Prospective participants will have their charts reviewed by referring providers to screen for exclusionary medical conditions and medications.

The study will be explained to eligible subjects by one of the clinician (PhD, MD, RN) investigators in a private setting. They will be informed of both the risks and benefits of the study. Potential subjects will be given ample opportunity to read the consent form and will be encouraged to ask questions. If a potential subject wishes to take the consent home to further consider participation, he or she will have that opportunity. Written informed consent will be obtained from subjects. The signed consent form will be placed in the subject's research record and a note documenting consent will be placed in the subject's computerized medical record.

If a potential subject's primary mental health care provider is a study investigator, another investigator will conduct the consent process. Care will be taken to assure subjects that their current treatment and future services and benefits are not contingent on participation in this or any research study. The voluntary nature of research study participation will be emphasized. Subjects will be informed that participation is voluntary and that their decision to participate or not will not effect their treatment at VA Puget Sound.

Participants will receive compensation for their time and inconvenience as follows: \$50 for the screening visit, \$50 for each cognitive testing day, \$200 for each LP day, and \$25 for each safety visit. The total each subject will receive if all study visits are completed is \$650. Subjects who withdraw early or are withdrawn from the study will receive pro-rated payments based on the number of study visits completed.

**(b) Protection Against Risk:**

*Reduction of risks related to simvastatin:* All study participants will have either normal or mildly elevated cholesterol not meeting current NCEP guidelines for treatment with cholesterol lowering medications. Simvastatin has been widely used for primary or secondary prevention of cardiovascular diseases. Although we will treat subjects with non-elevated cholesterol, adverse effects related to excessively low cholesterol levels are not anticipated, as recent trials with high doses of potent statins producing very low levels of LDL-cholesterol have shown that such low LDL-cholesterol serum levels are generally safe and, in fact, are associated with improved clinical outcomes in terms of coronary artery disease.

Simvastatin is classified by the US FDA as Pregnancy Category X and is contraindicated in women who are pregnant or nursing. All female subjects of child bearing potential will have urine pregnancy tests at every study visit and will be told of the risks of becoming pregnant while participating in this study. We consulted with pharmacist at VA Puget Sound whether a woman should wait for a certain period after ceasing statin drug before becoming pregnant and he suggested 16 days (the elimination half-life of radioactive simvastatin plus metabolites in humans is 4.5 hours. Assuming 95% of the drug and metabolites are eliminated after 5 half-lives, then 16 days could be considered safe). We are erring on the safe side and suggesting that women of childbearing potential wait one full menstrual cycle after stopping the medications offered in this study before becoming pregnant. Contraception is not required for male participants.

At randomization, subjects will be advised of potential drug-related side effects from simvastatin such as muscle pain and weakness and nausea or vomiting. They will be counseled on the importance of letting the study personnel know which medications they are currently taking and that they should inform the study staff before initiating any new medication treatment. Subjects will be told that many medications should not be taken with simvastatin and that they should not drink large quantities of grapefruit juice while in the study (as intake of large quantities of grapefruit juice may result in elevated simvastatin serum levels). Subjectst will also be advised to avoid drinking excessive amounts of alcohol.

Subjects will come to the research clinic for regular monitoring. At each visit, a qualified licensed clinician will ask subjects if they have experienced any adverse events, specifically if they have experienced any unexplained muscle pain, or weakness. Any adverse event will be reported to the PI, or if the PI is not available, an alternative MD investigator. Subjects will be encouraged to call a study clinician at any time if they are experiencing any side effects. Subjects will also be provided with 24-hour emergency contact information.

LFTs, CPK, and HbA1c levels will be measured at 6 weeks and after 3-, 6-, 9-, and 12- months of treatment. The PI will review the laboratory results for every subject within 24 hours of the study visit. If the PI is not available, an alternative MD practitioner will review the laboratory results. If SGOT or SGPT values are  $\geq 3$  times the upper limit of normal, or if CPK levels are  $\geq 10$  times the upper limit of normal, study drug will be discontinued and subjects will be followed until laboratory values return to normal.

To monitor for potential cognitive side effects, we will perform the MoCA (a brief but sensitive global cognitive test) at all safety visits. If a subject reports problems with memory or cognitive function after initiation of study medication sufficient to interfere with daily function or MoCA score decline of one standard deviation or greater compared to Baseline, we will perform a thorough neurological and psychiatric examination and will

administer the entire neuropsychological battery. If a decline of one standard deviation or greater compared to Baseline is present on any test, the subject will be terminated from the study.

To monitor for emergence or worsening of comorbid depression, the PHQ-9 will be administered at all visits. The PHQ-9 score can range from 0 to 27. Scores of 5, 10, 15 and 20 represent thresholds demarcating the lower limits of mild, moderate, moderately severe and severe depression, respectively. If the PHQ-9 score is increased by 10 (i.e., an increase of two severity categories) compared to baseline or if the subject develops suicidal ideation with intent, the subject will be terminated from the study. To monitor alcohol use and symptoms of comorbid PTSD, we will administer the AUDIT-C and the PCL-M at all visits.

Subjects who are discontinued for adverse events will be referred back to their primary medical provider for further assessment, treatment, and follow-up.

*Reduction of risks due to Lumbar Puncture:* Women of childbearing potential will have a negative urine pregnancy test before undergoing any LP procedures. Pain at the needle insertion site will be minimized by adequate local anesthesia with subcutaneous injection of 1% lidocaine. We will use an atraumatic 24g Sprotte spinal needle which is associated with a reduced risk of adverse events, including post-LP headache. The Sprotte needle has been recommended in published guidelines for reducing risk of post-LP headache. We have performed over 800 LPs since we began using the Sprotte spinal needle and in our hands, risk of post-LP headache is <1%.

We reduce the risk of CSF leak by having the subject lie in bed for one hour after the procedure, having them increase their fluid intake, and by instructing subjects not to engage in any strenuous activity for the 48 hours following the procedure. All investigators performing LPs are very experienced in performing this procedure in these subject populations.

Lastly, if the subject wishes, the subject's spouse, other family member, or friend may be present in the room during the LP, and is able to help keep the subject relaxed and comfortable.

*Reduction of risk due to venipuncture and i.v. placement:* All such procedures will be performed by experienced study staff using sterile technique.

*Reduction of risk due to loss of confidentiality:* We plan on obtaining a Federal Certificate of Confidentiality to protect against compelled disclosure of answers to the questionnaires. We will keep study records and data in a secure location, either in locked filing cabinets in locked rooms or on restricted-access, password-protected computers which meet all VA-mandated data security standards. Identifying information will not be stored with study data.

*Reduction of risks due to questionnaires and assessments:* To prevent the development of fatigue and/or unpleasant affective states due to the subject matter and the large number of individual tests, subjects will be able to take breaks between individual tests. Subjects are free to refuse to answer any question.

*Safety procedures specific to the war zone population:* include exclusion of participants with severe psychiatric instability or severe situational life crises, including evidence of being actively suicidal or homicidal, or any behavior that poses an immediate danger to patient or others. For participants enrolled in the study, requiring psychiatric interventions to manage deterioration of clinical status will result in early study termination, and appropriate crisis management by a study clinician, in conjunction with the participant's primary mental health care provider and referral to outpatient or inpatient psychiatric care at each study site. The PI (or back-up) will be on call at all times to receive calls from participants regarding any adverse events; participants will be provided with 24-hour emergency phone numbers.

In addition, due to the increased scrutiny surrounding studies of persons with comorbid depression, we will specifically ask about suicidal ideation at each study visit. Subjects who endorse suicidal ideation will be assessed as to their level of risk and the level of care required to keep themselves or others from harm. If a patient requires inpatient treatment in order to prevent harm but is unwilling to accept that care, referral will be made to the county-designated Mental Health Professional (MHP) and the patient will be supervised in a safe setting in the VA Puget Sound emergency room until evaluated by the MHP and appropriate disposition made. In a similar fashion, patients that are found to have symptoms of disorganized thought processes secondary to psychosis would be referred for an emergency psychiatric evaluation at VA Puget Sound.

*Treatment of Adverse events:* All treatment for adverse events related to the study will be provided free of charge. DVA authorizes treatment for any study approved by a VA R&D Committee. Subjects who seek treatment for study-related adverse events in a non-VA facility will be reimbursed for treatment costs. VA Puget Sound has adequate personnel and equipment to respond to expected and unexpected adverse events.

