**Monitoring safety of participants:** Simvastatin is used widely for lowering cholesterol and for primary prevention of cardiovascular and cerebrovascular disease at the doses proposed in this application. It is generally safe and well tolerated. The rate of adverse reactions necessitating withdrawal from statin therapy is <1% in clinical practice. The most common adverse effects in clinical use are elevated liver transaminases, myalgias, and elevated CPK. In our pilot study, all subjects tolerated a final simvastatin dose of 40mg/day. Of 24 subjects recruited, only two had significant adverse effects in response to statin therapy. One experienced significant myalgias requiring discontinuation of therapy despite a non-significant elevation in CPK. Another exhibited a slight increase in CPK with statin therapy. Mean serum CPK concentrations increased marginally over the course of the study. Mean SGOT and SGPT values increased equivalently. Only one subject developed a significant, though asymptomatic, elevation in SGPT. None of the subjects in our pilot study nor in our current placebo-controlled trial of simvastatin for primary prevention of AD experienced adverse cognitive changes or psychiatric symptoms.

Subjects will be advised of potential drug-related side effects such as muscle pain and weakness and nausea or vomiting at both the Screen (consent process) and Baseline visits. In addition, subjects will be monitored at 6 weeks and at 3-, 6-, 9-, and 12 months of treatment for potential adverse events. At each visit, we will review symptoms of anticipated adverse effects (such as muscle pain, weakness, and nausea), measure LFTs, CPK, and HbA1c, and (for female subjects of childbearing potential) conduct urine pregnancy tests.

To monitor for potential cognitive side effects, we will perform the MoCA (a brief but sensitive global cognitive test) at all safety visits. If a subject reports problems with memory or cognitive function after initiation of study medication sufficient to interfere with daily function or MoCA score decline of one standard deviation or greater compared to Baseline, we will perform a thorough neurological and psychiatric examination and will administer the entire neuropsychological battery. If a decline of one standard deviation or greater compared to Baseline is present on two neuropsychometric measures, the subject will be terminated from the study.

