To monitor for emergence or worsening of comorbid depression, the PHQ-9, a self-report measure of depression will be administered at all visits. The PHQ-9 score can range from 0 to 27. Scores of 5, 10, 15 and 20 represent thresholds demarcating the lower limits of mild, moderate, moderately severe and severe depression, respectively. If the PHQ-9 score is increased by 10 (i.e., an increase of two severity categories) compared to baseline, the subject will be terminated from the study. To monitor alcohol use and symptoms of comorbid PTSD, we will administer the AUDIT-C and the PCL-M at all visits.

If at any time during the study, a participant complains of symptoms which may indicate a potential adverse event, additional safety visit(s) as necessary will be performed. Procedures to be performed at additional visits will depend on the symptoms the participant is experiencing. If the participant meets any criterion for study removal (as described below), an early discontinuation visit will be performed.

**Early treatment discontinuation procedures:** The primary reasons for treatment discontinuation anticipated during the study are adverse effects, protocol violation, noncompliance, and withdrawal of consent. We will make every reasonable effort to keep each subject in the study. Every effort will be made to schedule a discontinuation visit as soon as possible following discontinuation of study medication to allow collection of outcome and safety measures.

**Criteria for termination from study:** Subjects will be removed from the study if they: 1) develop a significant adverse medication reaction, including psychiatric adverse effects; 2) exhibit >1 standard deviation decline on more than one component of the neuropsychological test battery; 3) develop a significant elevation in serum transaminases (i.e., > 3 X upper limit of normal for SGOT and/or SGPT) or CPK (i.e., > 10 X upper limit of normal); 4) have a positive urine pregnancy test; or 5) meet NCEP/ATP-III criteria for initiation of lipid-lowering therapy at the 3- or 6-month safety visits.

**Compliance with study medications:** Subjects will be given a 6-week supply of medication at Baseline and at the 6-week visit, and subjects will be given 3-month supplies of medication at the 3-, 6- and 9-month

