- Montreal Cognitive Assessment (MoCA): A cognitive assessment instrument designed to detect cognitive impairment and provides a brief assessment of global cognitive function, including short-term memory recall, executive function, sustained attention, calculation, language, and orientation. Scores range from 0-30 with lower scores indicating greater impairment. Test-retest reliability is high with less than one point variation. Internal consistency is good (Cronbach  $\alpha=0.83$ ). To correct for education, 1 point is added for those with less than 12 years of education.
- Wechsler Test of Adult Reading (WTAR): A neuropsychological test designed to provide estimates of premorbid intellectual functioning. This estimate is derived from the ability to read a list of irregular words, as single word reading recognition ability has been shown to be resilient to the effects of TBI.
- †WAIS-III Letter-Number Sequencing Subtest. The examiner reads a combination of numbers and letters that the subject is then asked to reproduce orally with the numbers first in ascending order, followed by the letters in alphabetical order. As the test progresses, items presented to the subject contain more numbers and letters. This test requires concentration, attention, and an ability to store and organize information in memory for a short duration (5-10 min.)
- †Grooved Pegboard: This is a test of fine motor coordination and speed. In this test, subjects are required to place 25 small metal pegs into holes on a 3" x 3" metal board. First the dominant hand is tested, and subjects are asked to place the pegs in the holes as fast as they can. This is repeated with the nondominant hand, and the total time for each hand is recorded. This test has been shown to be sensitive to statin manipulations.

- Auditory Consonant Trigrams: This is an adaptation of the Brown-Peterson technique. The task assesses short-term retention and due to the different lengths of interference activity, performance can be assessed at several difficulty levels. Three letters are read to the participant followed by a number. The subject begins to subtract from the number by threes until zero, three, nine, or 18 seconds have passed at which time the examiner asks the participant to recall the three letters. The test discriminates controls from persons with cognitive impairment.

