- Simple and Choice Reaction Time, Continuous Visual Memory Test, Digit Vigilance Test: These tests are part of a battery of computerized tests that was developed and validated in all adult age groups by the U.S. Department of the Navy to rapidly measure cognitive processing efficiency. In the simple reaction time task, symbols are presented on a computer screen and subjects are asked to strike a particular key on the keyboard as soon as a symbol appears. For the choice reaction time task, two different symbols appear at random on the screen and subjects are asked to respond to only one of the symbols. For the continuous performance test, numerous symbols appear on the screen and subjects are asked to respond to only one symbol when it is preceded by another particular symbol. For all subtests, this process is repeated ten times and the average of ten trials is used. Several studies have shown the battery to be sensitive to the effects of medications, including amphetamines and nicotine, and to mild head injury. It has good test-retest reliability and validity when compared to other well established tests.
- †Rey Auditory Verbal Learning Test (RAVLT): This is a brief verbal learning and memory instrument, consisting of a 15-item word list presented to the subject orally in five consecutive trials followed by a second list. The number of words recalled is recorded after each presentation of the list and the interference or second list. A delayed recall of the list is given followed by a yes/no recognition. It has excellent test-retest reliability (.51 - .70) and validity as demonstrated by a good correlation with other memory tests (.50 - .56).
- †Processing Speed Index from the WAIS-III: Based on 2 subtests of the WAIS-III: Digit Symbol and Symbol Search. For Digit Symbol, examinee must accurately fill in symbols according to matched number-symbol pairs in a key. For Symbol Search, examinee determines whether either of 2 target symbols match any of the symbols in a search group.
- †Digit Span of WAIS-III: A test of attention and memory from the WAIS-III.
- †Controlled Oral Word Association Test (COWAT): assesses the ability to quickly generate words beginning with certain letters. This test has been shown to be sensitive to the effects of frontal lobe dysfunction and to the effects of TBI: Total number of words generated will be used in this study.

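### The cognitive-decline removal rule is stated with two conflicting counts, and the lipid removal rule applies at two visits with no scheduled lipid panel

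*Combined protocol and SAP*

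**What the plan says.** **Cognitive rule.** The combined protocol and SAP states it three times.

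- Study procedures, Monitoring safety of participants: a cognitive complaint that interferes with daily life, or a sufficient MoCA drop, leads to a full examination and the whole battery. Termination then follows on this condition: "If a decline of one standard deviation or greater compared to Baseline is present on two neuropsychometric measures".
- Study procedures, Criteria for termination from study, item 2: subjects are removed if they "exhibit >1 standard deviation decline on more than one component of the neuropsychological test battery". No trigger is stated here.
- Protection of Human Subjects, (b) Protection Against Risk, Reduction of risks related to simvastatin: the lead-in and trigger are the same as in the safety-monitoring text, but the ending is "If a decline of one standard deviation or greater compared to Baseline is present on any test, the subject will be terminated from the study".

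Just before its list, Study procedures says: "If the participant meets any criterion for study removal (as described below), an early discontinuation visit will be performed".

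**Lipid rule.** Item 5 of the same list removes subjects who "meet NCEP/ATP-III criteria for initiation of lipid-lowering therapy at the 3- or 6-month safety visits". Table 3 marks the fasting lipid panel at screening, the first baseline visit and the first 12-month visit only.

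**The concern.** Both are mandatory removal rules, and the cognitive one is the plan's stated response to a risk that it discusses at length. Staff working from different sections could treat the same subject differently. If the wording in Protection Against Risk governs, the two-test wording elsewhere has no effect.

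The lipid rule depends on NCEP/ATP-III criteria, which the plan applies at entry through fasting LDL limits that vary with the number of risk factors. No new LDL value is scheduled at either visit the rule names.

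Removal also helps decide who is a completer, and the primary analysis is confined to completers. For the cognitive rule this route is narrow. The scheduled 12-month battery falls on the second outcome visit, after the outcome lumbar puncture, so only off-schedule batteries can cost a subject the primary endpoint.

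**Working it through.** **1. Cognitive rule, side by side**

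| Place | Count | Threshold | Unit | Trigger |
|---|---|---|---|---|
| Monitoring safety of participants | two | 1 SD or more | measure | complaint or MoCA drop |
| Criteria for termination, item 2 | more than one | above 1 SD | component | none stated |
| Protection Against Risk | any one | 1 SD or more | test | complaint or MoCA drop |

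There are two conflicting counts across three places. A subject with one qualifying decline meets the third rule and neither of the others. The first two do not say that such a subject must stay, so acting on the third breaches neither, but it makes their count redundant.

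The unit can change the result. The Processing Speed Index is "Based on 2 subtests of the WAIS-III: Digit Symbol and Symbol Search". For the Grooved Pegboard, "the total time for each hand is recorded". A drop on both Digit Symbol and Symbol Search, or with both hands, could be two measures but one component. No section says whether the SD is the between-subject SD at baseline, a normative SD or the SD of change.

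**2. Lipid rule against the schedule**

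- Table 3, fasting lipid panel: screening, first baseline, first 12-month visit. Nothing at 6 weeks or 3, 6 or 9 months.
- Safety-visit laboratory tests in Monitoring safety of participants and in Protection Against Risk: liver tests, CPK and HbA1c, with urine pregnancy tests where relevant. No lipids.

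Lipid panels scheduled at the two visits named in item 5: 0 of 2.

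**3. Illustration of how far the counts differ**

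This is per off-schedule battery and is not a trial-wide rate. The finding does not depend on it.

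Inputs from the plan:
- 13 measures from the instrument descriptions: letter-number sequencing, pegboard, consonant trigrams, simple and choice reaction time, continuous visual memory, digit vigilance, RAVLT, Digit Symbol, Symbol Search, digit span, COWAT and Trail Making. MoCA, WTAR and TOMM are left out.
- RAVLT retest reliability of .51 to .70, the only one stated for a battery test.

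Assumed: no true change, no retest gain, SD equal to the baseline SD, one common reliability r for all measures, and inter-test correlation of change of 0 to 0.3.

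Formulas: the SD of change is √(2(1−r)) baseline SDs, so the chance of a decline of 1 SD or more on one measure is p = Φ(−1/√(2(1−r))). For r = 0.80, √0.40 = 0.632 and p = Φ(−1.581) = 5.7%. With independent measures, P(at least one) = 1 − (1−p)^13 and P(exactly one) = 13p(1−p)^12. P(two or more) is the difference between them. For r = 0.80 these are 53.3%, 36.6% and 16.7%. At correlation 0.3, the same quantities come from a one-factor normal model.

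| Case | p, one measure | Any test | Two or more | Exactly one (counts disagree) |
|---|---|---|---|---|
| r = 0.51 | 15.6% | 89.0 / 69.9% | 62.6 / 47.5% | 26.5 / 22.4% |
| r = 0.70 | 9.8% | 74.0 / 55.0% | 37.1 / 31.3% | 36.9 / 23.7% |
| r = 0.80 | 5.7% | 53.3 / 39.1% | 16.7 / 17.8% | 36.6 / 21.3% |
| r = 0.90 | 1.3% | 15.3 / 12.3% | 1.1 / 2.9% | 14.1 / 9.4% |
| SD of change, any r | 15.9% | 89.4 / 70.4% | 63.5 / 48.1% | 25.9 / 22.3% |

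Each pair is correlation 0 / 0.3. The last row shows why the SD must be named: if it is the SD of change, p = Φ(−1) whatever the reliability. Counting the Processing Speed Index as one measure (12 in all) at r = 0.80 gives 50.5 / 37.4% for any test and 14.7 / 16.4% for two or more.

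**The case against.** **The termination list governs.** It is headed as such, the text before it points to it, and the safety-monitoring text agrees with its count. On this view the Protection Against Risk sentence is a loose restatement. That is a fair guess at intent, but the sentence is equally mandatory, it sits in the section that tells reviewers how subjects are protected, and no order of precedence is given.

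**Subjects are protected either way.** The examination follows the trigger in both descriptions, and item 1 of the list removes anyone with a significant adverse reaction. This limits the harm. It does not settle what happens to a subject with one decline.

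**The lipid rule is not wholly inoperable.** Entry limits are LDL below 190 with at most one risk factor and below 160 with two or more. A subject with a known LDL of 160 to 189 whose risk-factor count rises would cross the limit without a new panel. The Biomarkers section describes the lumbar-puncture-day bloods without saying there are no others, and the safety-visit paragraph defers its assessments to later text. This stands, so the claim is limited to what is scheduled. Nor is any effect of this gap on the analysis set shown, since scheduled lipid data would remove nobody at those visits.

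**The percentages are mostly assumption.** This also stands. Any test runs from 12% to 89% across the table, splitting the Processing Speed Index but not the pegboard is a choice, and subjects sent for a battery are selected by complaint or MoCA drop, so no true change does not describe them. The difference between above 1 SD and 1 SD or more is a drafting point.

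**Conclusion.** The concern holds in both parts, on the current text. The cognitive removal rule contradicts itself on the count, with its SD and unit undefined. The lipid removal rule names two visits at which no lipid panel is scheduled. Both need correcting because they are mandatory subject-protection rules that cannot be applied uniformly as written.

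The size that needs no assumption is two counts across three places, and 0 of 2 panels. Under the stated assumptions at reliability 0.80 to 0.90, the two counts would classify a subject differently in about 9% to 37% of off-schedule batteries. The plan does not say how often such batteries will occur, so no trial-wide figure follows. No bias or loss of power is claimed. A planned early-discontinuation visit and a secondary mixed model that includes early terminators soften any effect on the analysis.

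**What to change.** Reconcile Monitoring safety of participants, Criteria for termination from study (item 2) and Protection Against Risk so that a single cognitive-decline criterion appears in all three. It should state the count, the threshold, which SD is meant, the counting unit (including how the Processing Speed Index and the two pegboard hands are counted) and whether the complaint or MoCA trigger must come first. Reconcile item 5 of the termination list with Table 3 and the safety-visit laboratory lists. Which rules stand is for the clinical team to decide. The statistician can tabulate the chance-trigger rate of the chosen cognitive rule, but this is optional.

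The cost is a protocol wording amendment, with no additional patients.
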